## 6. SAFETY REPORTING AND MEDICAL MANAGEMENT

The Principal Investigator is responsible for ensuring that all staff involved in the study are familiar with the content of this section.

## 6.1 Definition of adverse events

An adverse event is the development of an undesirable medical condition or the deterioration of a pre-existing medical condition following or during exposure to a pharmaceutical product, whether or not considered causally related to the product. An undesirable medical condition can be symptoms (e.g., nausea, chest pain), signs (e.g., tachycardia, enlarged liver) or the abnormal results of an investigation (e.g., laboratory findings, electrocardiogram). In clinical studies, an AE can include an undesirable medical condition occurring at any time, including run-in or washout periods, even if no study treatment has been administered.

The term AE is used to include both serious and non-serious AEs.

## 6.2 Definitions of serious adverse event

A serious adverse event is an AE occurring during any study period (i.e., run-in, treatment, follow-up), that fulfils one or more of the following criteria:

- Results in death
- Is immediately life-threatening
- Requires in-patient hospitalisation or prolongation of existing hospitalisation
- Results in persistent or significant disability/incapacity or substantial disruption of the ability to conduct normal life functions
- Is a congenital abnormality or birth defect
- Is an important medical event that may jeopardise the subject or may require medical intervention to prevent one of the outcomes listed above.

For further guidance on the definition of a SAE, see Appendix B to the Clinical Study Protocol.

## 6.3 Recording of adverse events

### 6.3.1 Time period for collection of adverse events

Adverse Events will be collected from the time the subject signs the informed consent form, throughout the treatment period and till end of follow-up period at FU 2 Visit.

### 6.3.2 Follow-up of unresolved adverse events

AEs that are unresolved at the time of telephonic FU 2 Visit (or on-site FU 2 visit for WOCBP) will be followed up by the Investigator for as long as medically indicated, but without further recording in the eCRF. If deemed necessary and depending on their judgement, Principal Investigator may even call the subject for an on-site visit for further evaluation. AstraZeneca retains the right to request additional information for any subject with ongoing AE(s)/SAE(s) at the end of the study, if judged necessary.

## 6.3.3 Variables

The following variables will be collected for each AE;

- AE (verbatim)
- The date when the AE started and stopped
- Maximum intensity of the AE
- Whether the AE is serious or not
- Investigator causality rating against the Investigational Product (yes or no)
- Action taken with regard to investigational product
- Outcome.

### *Intensity rating scale:

- 1 mild (awareness of sign or symptom, but easily tolerated)
- 2 moderate (discomfort sufficient to cause interference with normal activities)
- 3 severe (incapacitating, with inability to perform normal activities)

In addition, the following variables (if applicable) will be collected in eCRF for SAEs:

- Date AE met criteria for serious AE
- Date Investigator became aware of serious AE
- AE is serious due to
- Date of hospitalisation
- Date of discharge
- Probable cause of death
- Date of death
- Autopsy performed
- Causality assessment in relation to Study procedure(s)
- Description of AE.

It is important to distinguish between serious and severe AEs. Severity is a measure of intensity whereas seriousness is defined by the criteria in Section 6.2. An AE of severe intensity need not necessarily be considered serious. For example, nausea that persists for several hours may be considered severe nausea, but not a SAE unless it meets the criteria shown in Section 6.2. On the other hand, a stroke that results in only a limited degree of disability may be considered a mild stroke but would be a SAE when it satisfies the criteria shown in Section 6.2.

## 6.3.4 Causality collection

The Investigator will assess causal relationship between investigational product and each AE, and answer 'yes' or 'no' to the question 'Do you consider that there is a reasonable possibility that the event may have been caused by the investigational product?'

For SAEs causal relationship will also be assessed for other medication and study procedures. Note that for SAEs that could be associated with any study procedure the causal relationship is implied as 'yes'.

A guide to the interpretation of the causality question is found in Appendix B to the Clinical Study Protocol.

## 6.3.5 Adverse events based on signs and symptoms

All AEs spontaneously reported by the subject or reported in response to the open question from the study personnel: *'Have you had any health problems since the previous visit/you were last asked?'*, or revealed by observation will be collected and recorded in the eCRF. When collecting AEs, the recording of diagnoses is preferred (when possible) to recording a list of signs and symptoms. However, if a diagnosis is known and there are other signs or symptoms that are not generally part of the diagnosis, the diagnosis and each sign or symptom will be recorded separately.

## 6.3.6 Adverse events based on examinations and tests

The results from protocol mandated laboratory tests and vital signs will be summarised in the CSR. Deterioration as compared to baseline in protocol-mandated laboratory values, vital signs should therefore only be reported as AEs if they fulfil any of the SAE criteria or are the reason for discontinuation of treatment with the investigational product.

If deterioration in a laboratory value/vital sign is associated with clinical signs and symptoms, the sign or symptom will be reported as an AE and the associated laboratory result/vital sign will be considered as additional information. Wherever possible the reporting Investigator uses the clinical, rather than the laboratory term (e.g., anaemia versus low haemoglobin value). In the absence of clinical signs or symptoms, clinically relevant deteriorations in non-mandated parameters should be reported as AE(s).

Any untoward findings or events encountered during or after the conduct of study procedures that are not related to the disease under investigation will be reported as an AE(s)/SAE(s).

Deterioration of a laboratory value, which is unequivocally due to disease progression, should not be reported as an AE/SAE.

Any new or aggravated clinically relevant abnormal medical finding at a physical examination as compared with the baseline assessment will be reported as an AE.

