#### Table 2Laboratory safety variables

Tests	Variables
Haematology/Haemostasis (whole blood)	Haemoglobin, Red blood cell (RBC) count, Leukocyte count, Leukocyte differential count (absolute count), Platelet count, Haematocrit, Mean corpuscular volume
Clinical chemistry (Serum)	Alkaline phosphatase (ALP), Alanine transaminase (ALT), Aspartate transaminase (AST), Bilirubin (Total), Blood urea nitrogen, Calcium (Total), Carbon dioxide (CO ₂ ), Chloride, Creatinine, Creatinine kinase, C- Reactive Protein (CRP), Gamma-glutamyl transpeptidase (GGT), Glucose, Phosphorus, Potassium, Sodium, Total cholesterol, Uric acid
Urine (Dipstick)	Nitrite, Bilirubin, Glucose, Blood, Protein, Ketones
Urine ¹	Microscopy, Casts, Culture (as required)

1. Urine samples will be collected and sent for analysis at the central lab only when a positive dipstick result for any parameter is observed

Blood samples for determination of haematology/haemostasis and clinical chemistry will be performed at a central laboratory. For information on methods of collection, assessment, labelling, storage and shipment of samples please refer to the separate laboratory Manual.

The Investigator should make an assessment of the available results with regard to clinically relevant abnormalities. The laboratory results report should be signed and dated, and retained at site as source data for laboratory variables. For information on how AEs based on laboratory tests should be recorded and reported, see Section 6.3.

**NB.** In case a subject shows an AST or ALT  $\ge 3xULN$  and total bilirubin  $\ge 2xULN$  please refer to Appendix D 'Actions required in cases of combined increase of Aminotransferase and Total Bilirubin – Hy's Law', for further instructions.

The total volume of blood that will be collected from each subject during the study is presented in Table 3.

Assessment ³		Sample volume (mL)	No. of samples	Total volume ² (mL)
Safety	Clinical chemistry	2.5	2	5
	Haematology	2	4	8
FSH, β-HCG ¹		1	1	1
Serology		7.5	1	7.5
IgE		2.5	3	7.5

Table 3Volume of blood to be drawn from each subject

Assessment ³	Sample volume (mL)	No. of samples	Total volume ² (mL)
Phadiatop	2.5	1	2.5
Serum biomarkers	16	3	48
РК	3.5	2	7
ADA/nAb	3.5	2	7
		Total	93.5

1. Female subjects only

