## 5.2.5 Vital signs

Vital signs (i.e., pulse, blood pressure, respiration rate and body temperature) will be obtained in accordance with the schedule provided in Table 1. Vital signs will be taken prior to blood drawing and IP administration. At Visits 3c through 6, subjects should be observed for a minimum of 2 hours after IP administration for the appearance of any acute drug reactions. For the remaining visits involving IP administration, subjects will be observed for a minimum of 1 hour after IP administration for any such reaction. Any new finding(s) or aggravated existing finding(s), judged as clinically significant by the Investigator, will be reported as an AE as described in Section 6.1.

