#### **3.4.2** Safety topics of special attention

Although the CSP did not describe AEs of special interest, AstraZeneca Patient Safety and study physicians will review all AEs and identify those that merit special attention. These AEs fall into three categories, AEs possibly related to administration of biologics (e.g., anaphylaxis/hypersensitivity reactions and injection site reactions), AEs possibly related to the mechanism of action of tralokinumab as an IL-13 blocking agent (e.g., infections such as

severe, viral, invasive fungal, and parasitic, malignancy, cardiovascular/cerebrovascular events, pregnancy/spontaneous abortion and increased eosinophils) and AEs reported for other biologics in this class (e.g., musculoskeletal). AEs falling into the category of safety topics of special attention will be tabulated.

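### Protocol 5.2.5 and 6.3.6 give sites different AE rules for vital signs; separately, 6.3.6 keeps asymptomatic, non-serious eosinophil rises out of the SAP's AE-based eosinophil topic

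*Protocol*

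**What the plan says.** **Vital signs.** Protocol 5.2.5 states: "Any new finding(s) or aggravated existing finding(s), judged as clinically significant by the Investigator, will be reported as an AE". It refers the site to 6.1 for the definition of an AE, and 6.1 includes "abnormal results of an investigation (e.g., laboratory findings, electrocardiogram". Protocol 6.3.6 explains that mandated laboratory and vital-sign results are summarised in the study report, and draws from this that they "vital signs should therefore only be reported as AEs if they fulfil any of the SAE criteria or are the reason for discontinuation" of IP.

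**Laboratory values.** The same sentence in 6.3.6 opens with "Deterioration as compared to baseline in protocol-mandated laboratory values", so laboratory values fall under the same limit. When clinical signs or symptoms are present, "the sign or symptom will be reported as an AE and the associated laboratory result/vital sign will be considered as additional information". Protocol 5.2.1 sets no rule of its own for laboratory AEs: "For information on how AEs based on laboratory tests should be recorded and reported, see Section 6.3".

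**Safety topics.** SAP 3.4.2 has the sponsor's safety and study physicians review all AEs and pick out those that merit special attention. The examples linked to the mechanism of action end with "pregnancy/spontaneous abortion and increased eosinophils". AEs in these topics are then tabulated, and SAP 4.2.9.1 includes the topic category among the summaries by system organ class and preferred term. Protocol 8.4.5.2 draws other significant AEs (OAEs) from AEs that are neither serious nor a cause of discontinuation, and gives marked haematological abnormalities as an example. SAP Section 6 says that the OAEs have become the safety topics.

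**The concern.** Two separate things go wrong.

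First, a site that follows 5.2.5 and a site that follows 6.3.6 will record the same vital-sign finding differently. With about 20 to 25 sites, the AE frequency for such findings then depends partly on which page each site used.

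Second, the SAP names raised eosinophils as a topic but fills it from a source that the protocol has largely closed to asymptomatic laboratory changes. The topic matters because the effect is expected. Protocol 1.1 reports that blood eosinophils rose on tralokinumab in earlier trials, and 1.1 and 1.3 make a rise part of the hypothesis under test. A low count in the topic row would partly reflect the reporting rule, and neither SAP 3.4.2 nor 4.2.9.1 says so or points to the laboratory results.

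**Working it through.** No arithmetic applies: the documents give no expected number of vital-sign or eosinophil AEs. The check sets the rules side by side.

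**Vital signs.** Take a new finding that the investigator judges clinically significant.

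| Situation | Protocol 5.2.5 | Protocol 6.3.6 |
|---|---|---|
| Meets an SAE criterion | AE | AE |
| Is the reason for stopping IP | AE | AE |
| Has symptoms, not serious, IP continues | the finding is an AE | the symptom is the AE; the reading supports it |
| No symptoms, not serious, IP continues | AE | not an AE |

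The last line is a direct conflict. The cross-references do not resolve it, because 5.2.5 sends the site to the general definition in 6.1 and not to 6.3.6. The conflict is confined to vital signs. Protocol 5.2.3 and 5.2.4 use similar wording for physical examination and ECG, but 6.3.6 itself makes clinically relevant new examination findings AEs, and its restriction does not mention ECGs.

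**Eosinophils.**

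1. Is the count protocol-mandated? Yes. Protocol 5.1.14 takes it from the scheduled haematology sample, and the differential count is listed in Table 2. The 6.3.6 exception for non-mandated parameters therefore does not apply.
2. Which AE rule governs? Protocol 5.2.1 defers to 6.3, so 6.3.6 does. There is no competing laboratory rule and no conflict with 5.2.5.
3. Which rises can become AEs? Those that meet an SAE criterion and those that stop IP. In a symptomatic case, the symptom or a clinical diagnosis is reported. Eosinophilia appears among the withdrawal criteria in 3.9.2 only in combination with raised ALT or AST, so a rise alone is not a listed reason to withdraw.
4. Which rises cannot? Asymptomatic, non-serious rises with IP continued.
5. What feeds the SAP topic? Reported AEs only. The rises in step 4 therefore cannot enter it.
6. Do OAEs offer another route? No. Protocol 8.4.5.2 selects AEs that are neither serious nor discontinuations. For an asymptomatic mandated laboratory value, 6.3.6 admits only those that are serious or stop IP. The two sets do not overlap.

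**Where the rises are reported.** SAP 4.2.5.1 analyses the blood eosinophil count as a secondary endpoint, with a repeated-measures model for the ratio to baseline, summaries by visit, and listings. SAP 4.2.9.2 gives laboratory summaries, shift tables from baseline to the on-treatment extreme, shift plots and frequencies of noteworthy values. SAP 3.1.4 includes unscheduled values in the extremes.

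**The case against.** The limit in 6.3.6 is deliberate and explained: results that will be summarised as data need not be reported again as AEs. That is a coherent choice, and nothing here asks for it to be dropped.

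Eosinophils are also among the most fully reported measurements in the trial, and the laboratory section of the SAP directly follows the AE section. A reader might infer that the plan hides an eosinophil signal, or that the topic table gives false reassurance. The documents do not support this: the expected rise is stated openly, and it is analysed as a secondary endpoint.

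SAP 3.4.2 can fairly be read as medical review of whatever AEs are reported, with eosinophils as one example. Serious cases, cases that stop IP, and clinical diagnoses can still appear, so a claim that the topic must be empty goes too far.

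For vital signs, SAP 4.2.9.5 summarises the measurements independently of AEs. Differences between sites in a blinded, randomised trial give no evident reason to expect bias towards one arm.

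Two things still stand after this. Sections 5.2.5 and 6.3.6 cannot both be followed for the same vital-sign finding. And the SAP names an expected laboratory effect as a topic without saying that its AE source leaves out the asymptomatic, non-serious cases.

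**Conclusion.** The point holds and is minor. It concerns the consistency of AE recording and the reading of one safety topic. The primary and secondary efficacy analyses are not affected.

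The vital-sign conflict rests on the text alone. The eosinophil point rests on two readings: that the differential count is a protocol-mandated laboratory value, and that the topic is filled from AEs as SAP 3.4.2 describes. Under those readings the row will under-represent rises.

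By how much cannot be said. A number of missing subjects would need an assumed rate of marked rises and an assumed rate of AE reporting, and the documents give neither.

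A reader might also infer that the laboratory limit contradicts 5.2.5. It does not: 5.2.5 concerns vital signs, and the laboratory section defers to 6.3. For laboratory values the mismatch lies between 6.3.6 and two later definitions, the SAP topic and the OAE examples in Protocol 8.4.5.2.

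**What to change.** 1. Reconcile Protocol 5.2.5 and 6.3.6 so that both state one and the same AE reporting rule for vital signs. Which rule to keep is for the sponsor to decide. Cost: one sentence and a reminder to sites.

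2. In SAP 3.4.2 and 4.2.9.1, add to the eosinophil topic the number and percentage of subjects per arm whose central-laboratory eosinophil count exceeds the upper reference limit. Show this at Week 6, at Week 12, and for the on-treatment maximum including unscheduled values, beside any reported AEs. Name the reference range used, since SAP 3.4.3 and 4.2.9.2 refer to different ones. Add a cross-reference to 4.2.9.2, where the shift tables show baseline status. Cost: one extra table from data already collected. This step needs no protocol change and can be made at any time before unblinding.

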## 6.3.7 Hy's Law

Cases where a subject shows elevations in liver biochemistry may require further evaluation and occurrences of AST or  $ALT \ge 3xULN$  together with total bilirubin  $\ge 2xULN$  may need to be reported as SAEs. Please refer to Appendix D for further instruction on cases of increases in liver biochemistry and evaluation of Hy's Law.

### 6.3.8 Disease progression

### Symptoms of the disease under study

Asthma symptoms or signs, such as, wheeze, cough, chest tightness, dyspnoea, breathlessness and phlegm, will be recorded as AEs when:

- $\circ$  the sign or symptom is serious according to definitions, see Section 6.2
- the subject discontinues the study due to the sign or symptom, and/or
- the sign or symptom is new to the subject or not consistent with the subject's preexisting asthma history (defined as within 1 year of Visit 1) as judged by the Investigator.

Asthma exacerbations should not be recorded as AEs after randomization, unless it fulfils any of the above criteria. All asthma exacerbations should be recorded in the exacerbation eCRF as per Section 5.1.12.

If a subject discontinues IP due to a study specific discontinuation criterion, this should always be recorded as 'Development of study specific withdrawal' on the termination form in the eCRF. In addition, the Investigator must assess whether the asthma deterioration should also be reported as an AE leading to discontinuation of IP (DAE)/AE leading to withdrawal from study on the AE form.

## 6.4 **Reporting of serious adverse events**

All SAEs have to be reported, whether or not considered causally related to the investigational product, or to the study procedure(s). All SAEs will be recorded in the eCRF.

If any SAE occurs in the course of the study, then Investigators or other site personnel inform the appropriate AstraZeneca representatives within one day i.e., immediately but **no later than 24 hours** of when he or she becomes aware of it.

The designated AstraZeneca representative works with the Investigator to ensure that all the necessary information is provided to the AstraZeneca Patient Safety data entry site within 1 calendar day of initial receipt for fatal and life threatening events and within 5 calendar days of initial receipt for all other SAEs.

For fatal or life-threatening adverse events where important or relevant information is missing, active follow-up is undertaken immediately. Investigators or other site personnel inform AstraZeneca representatives of any follow-up information on a previously reported SAE within one calendar day i.e., immediately but **no later than 24 hours** of when he or she becomes aware of it.

Once the Investigators or other site personnel indicate an AE is serious in the WBDC system, an automated email alert is sent to the designated AstraZeneca representative(s). If the WBDC system is not available, then the Investigator or other study site personnel reports a SAE to the appropriate AstraZeneca representative(s) by telephone. The AstraZeneca representative(s) will advise the Investigator/study site personnel how to proceed.

The reference document for definition of expectedness/listedness is the Investigator's Brochure for the AstraZeneca IP.

## 6.5 Overdose

An overdose with associated AEs is recorded as the AE diagnosis/symptoms on the relevant AE modules in the eCRF and on the Overdose eCRF module. An overdose without associated symptoms is only reported on the Overdose eCRF module.

If an overdose on an AstraZeneca study drug occurs in the course of the study, then the Investigator or other site personnel inform appropriate AstraZeneca representative(s) immediately, or **no later than 24 hours** of when he or she becomes aware of it.

The designated AstraZeneca representative(s) will work with the Investigator to ensure that all relevant information is provided to the AstraZeneca Subject Safety data entry site.

For overdoses associated with a SAE, the standard reporting timelines apply, see Section 6.4. For other overdoses, reporting must occur within 30 days.

## 6.6 Pregnancy

All pregnancies and outcomes of pregnancy should be reported to AstraZeneca.

## 6.6.1 Maternal exposure

If a subject becomes pregnant during the course of the study investigational product should be discontinued immediately.

Pregnancy itself is not regarded as an adverse event unless there is a suspicion that the investigational product under study may have interfered with the effectiveness of a contraceptive medication. Congenital abnormalities/birth defects and spontaneous miscarriages should be reported and handled as SAEs. Elective abortions without complications should not be handled as AEs. The outcome of all pregnancies (spontaneous miscarriage, elective termination, ectopic pregnancy, normal birth or congenital abnormality) should be followed up and documented even if the subject was discontinued from the study.

If any pregnancy occurs in the course of the study, then the Investigator or other site personnel informs the appropriate AstraZeneca representative(s) within 1day i.e., immediately but **no later than 24 hours** of when he or she becomes aware of it.

The designated AstraZeneca representative(s) will work with the Investigator to ensure that all relevant information is provided to the AstraZeneca Patient Safety data entry site within 1 or 5 calendar days for SAEs (see Section 6.4) and within 30 days for all other pregnancies.

The same timelines apply when outcome information is available.

The pregnancy module in the eCRF will be used to report the pregnancy and the pregnancy outcome module will be used to report the outcome of the pregnancy.

